# with ≥1 encounter			
Mean			
Standard deviation			
Minimum			

Maximum			
Median (range across sites)			
Emergency department encounters			
Total # of encounters per arm (N)			
# with ≥1 encounter			
Mean			
Standard deviation			
Minimum			
Maximum			
Median (range across sites)			
Hospital admissions			
Total # of encounters per arm (N)			
# with ≥1 encounter			
Mean			
Standard deviation			
Minimum			
Maximum			
Median (range across sites)			
Institutional stays			
Total # of encounters per arm (N)			
# with ≥1 encounter			
Mean			
Standard deviation			
Minimum			
Maximum			
Median (range across sites)			
Number of days hospitalized			
Mean			
Standard deviation			
Minimum			
Maximum			
Median (range across sites)			
Total # of days hospitalized per arm			NA

Table 1S. Baseline characteristics of all patients in the as-randomized analysis by early intervention vs. delayed intervention (sensitivity analysis)

	Overall (N=XXXX)	Early intervention (N=XXXX)	Delayed intervention (N=XXXX)	p-value	Stand. mean difference (%)
Demographics					
Age					
N					
Mean (SD)					
Median (Min, 25 th , 75 th , Max)					

	Overall (N=XXXX)	Early intervention (N=XXXX)	Delayed intervention (N=XXXX)	p-value	Stand. mean difference (%)
30-34 yr, %					
35-39, %					
40-44, %					
45-49, %					
50-54, %					
55-59, %					
60-64, %					
65-69, %					
70-74, %					
75-79, %					
≥ 80, %					
Sex					
N					
Female, %					
Region					
New England, %					
Mid-Atlantic, %					
South-Atlantic, %					
Midwest, %					
Mountain, %					
Pacific, %					
Unknown, %					
Medical history					
History of anemia?					
N					
Yes, %					
History of hypertension?					
N					
Yes, %					
History of diabetes?					
N					
Yes, %					
History of hospitalization for any bleeding?					
N					
Yes, %					
History of peripheral vascular disease?					
N					
Yes, %					
History of prior cerebrovascular disease?					
N					
Yes, %					

	Overall (N=XXXX)	Early intervention (N=XXXX)	Delayed intervention (N=XXXX)	p-value	Stand. mean difference (%)
History of heart failure?					
N					
Yes, %					
History of kidney disease?					
N					
Yes, %					
History of MI					
N					
Yes, %					
History of CABG					
N					
Yes, %					
History of coronary stent					
N					
Yes, %					
CHA ₂ DS ₂ VASc score					
N					
Mean (SD)					
Median (25th, 75th)					
0, %					
1, %					
2, %					
3, %					
4, %					
5, %					
6, %					
7, %					
8, %					
9, %					
Bleeding risk score: ATRIA score					
Low (≤ 3), %					
Intermediate (4), %					
High (≥ 5), %					
Hospitalization in the prior 6 months					
0, %					
1, %					
2, %					
≥ 3 , %					
Mean (SD) follow up time					
Minimum follow up time					
Maximum follow up time					
Median follow up time (range across sites)					

Table 2S. – Odds ratio of one OAC dispensing or 4 or more INRs (primary endpoint) over the course of the 12-months of follow-up: early intervention vs. delayed intervention – as-randomized analysis (sensitivity analysis)

	Early Intervention, n/N (%)	Delayed Intervention, n/N (%)	Unadj. Parameter Estimate (SE)	Unadj. Odd Ratio (95% CI)	Adj. Parameter Estimate (SE)	Adj. Odds Ratio (95% CI)	p-value for adjusted OR
OAC dispensing or ≥4 INRs at 365 days							

B. CONSORT 2010 WORKSHEET FOR RANDOMIZED TRIALS

CONSORT 2010 checklist of information to include when reporting a randomized trial

Section/Topic	Item No	Checklist item	Reported on page No
Title and abstract			
	1a	Identification as a randomized trial in the title	
	1b	Structured summary of trial design, methods, results, and conclusions (for specific guidance see CONSORT for abstracts)	
Introduction			
Background and objectives	2a	Scientific background and explanation of rationale	
	2b	Specific objectives or hypotheses	
Methods			
Trial design	3a	Description of trial design (such as parallel, factorial) including allocation ratio	
	3b	Important changes to methods after trial commencement (such as eligibility criteria), with reasons	
Participants	4a	Eligibility criteria for participants	
	4b	Settings and locations where the data were collected	
Interventions	5	The interventions for each group with sufficient details to allow replication, including how and when they were actually administered	
Outcomes	6a	Completely defined pre-specified primary and secondary outcome measures, including how and when they were assessed	
	6b	Any changes to trial outcomes after the trial commenced, with reasons	
Sample size	7a	How sample size was determined	
	7b	When applicable, explanation of any interim analyses and stopping guidelines	
Randomisation:			
Sequence generation	8a	Method used to generate the random allocation sequence	
	8b	Type of randomization; details of any restriction (such as blocking and block size)	
Allocation concealment mechanism	9	Mechanism used to implement the random allocation sequence (such as sequentially numbered containers), describing any steps taken to conceal the sequence until interventions were assigned	
Implementation	10	Who generated the random allocation sequence, who enrolled participants, and who assigned participants to interventions	
Blinding	11a	If done, who was blinded after assignment to interventions (for example, participants, care providers, those assessing outcomes) and how	
	11b	If relevant, description of the similarity of interventions	

Section/Topic	Item No	Checklist item	Reported on page No
Statistical methods	12a	Statistical methods used to compare groups for primary and secondary outcomes	
	12b	Methods for additional analyses, such as subgroup analyses and adjusted analyses	
Results			
Participant flow (a diagram is strongly recommended)	13a	For each group, the numbers of participants who were randomly assigned, received intended treatment, and were analyzed for the primary outcome	
	13b	For each group, losses and exclusions after randomization, together with reasons	
Recruitment	14a	Dates defining the periods of recruitment and follow-up	
	14b	Why the trial ended or was stopped	
Baseline data	15	A table showing baseline demographic and clinical characteristics for each group	
Numbers analysed	16	For each group, number of participants (denominator) included in each analysis and whether the analysis was by original assigned groups	
Outcomes and estimation	17a	For each primary and secondary outcome, results for each group, and the estimated effect size and its precision (such as 95% confidence interval)	
	17b	For binary outcomes, presentation of both absolute and relative effect sizes is recommended	
Ancillary analyses	18	Results of any other analyses performed, including subgroup analyses and adjusted analyses, distinguishing pre-specified from exploratory	
Harms	19	All important harms or unintended effects in each group (for specific guidance see CONSORT for harms)	
Discussion			
Limitations	20	Trial limitations, addressing sources of potential bias, imprecision, and, if relevant, multiplicity of analyses	
Generalizability	21	Generalizability (external validity, applicability) of the trial findings	
Interpretation	22	Interpretation consistent with results, balancing benefits and harms, and considering other relevant evidence	
Other information			
Registration	23	Registration number and name of trial registry	
Protocol	24	Where the full trial protocol can be accessed, if available	
Funding	25	Sources of funding and other support (such as supply of drugs), role of funders	

C. ICD-10 CODES FOR DEFINING CLINICAL OUTCOMES

The below ICD-10-CM codes will be used to define clinical outcomes during analyses (list is not final).

- a. **Ischemic stroke or unknown stroke:** diagnosis of
 1. I63.x Cerebral infarction, including
 - i. I63.0 Cerebral infarction due to thrombosis of precerebral arteries
 - ii. I63.1 Cerebral infarction due to embolism of precerebral arteries
 - iii. I63.2 Cerebral infarction due to unspecified occlusion or stenosis of precerebral arteries
 - iv. I63.3 Cerebral infarction due to thrombosis of cerebral arteries
 - v. I63.4 Cerebral infarction due to embolism of cerebral arteries
 - vi. I63.5 Cerebral infarction due to unspecified occlusion or stenosis of cerebral arteries
 - vii. I63.6 Cerebral infarction due to cerebral venous thrombosis, nonpyogenic
 - viii. I63.8 Other cerebral infarction
 - ix. I63.9 Cerebral infarction, unspecified
 2. I67.81 Acute cerebrovascular insufficiency
 3. I67.82 Cerebral ischemia
 4. I67.89 Other cerebrovascular disease
 5. I67.9 Cerebrovascular disease, unspecified
 6. G45.x Transient cerebral ischemic attacks and related syndromes, including
 - i. G45.0 Vertebro-basilar artery syndrome
 - ii. G45.1 Carotid artery syndrome (hemispheric)
 - iii. G45.2 Multiple and bilateral precerebral artery syndromes
 - iv. G45.3 Amaurosis fugax
 - v. G45.4 Transient global amnesia
 - vi. G45.8 Other transient cerebral ischemic attacks and related syndromes
 - vii. G45.9 Transient cerebral ischemic attack, unspecified
 7. without primary diagnosis of Intracranial injury (S06.x)
- b. **Hemorrhagic stroke:** diagnosis of
 1. I60.x Nontraumatic subarachnoid hemorrhage
 2. I61.x Nontraumatic intracerebral hemorrhage
 3. I62.x Other and unspecified nontraumatic intracranial hemorrhage
 4. without primary diagnosis of Intracranial injury (S06.x)
- c. **Hospitalization for any bleeding:** see ICD-10-CM codes in “any hemorrhage” category in [cohort identification code list](#) (of which GI bleeding is a subset)
- d. **Hospitalization for GI bleeding:**
 1. I85.01 Esophageal varices with bleeding
 2. I85.11 Secondary esophageal varices with bleeding
 3. K22.11 Ulcer of esophagus with bleeding
 4. K22.6 Gastro-esophageal laceration-hemorrhage syndrome
 5. Gastric ulcer
 - i. K25.0 Acute with hemorrhage
 - ii. K25.2 Acute with hemorrhage and perforation
 - iii. K25.4 Chronic or unspecified with hemorrhage
 - iv. K25.6 Chronic or unspecified with hemorrhage and perforation
 6. Duodenal ulcer
 - i. K26.0 Acute with hemorrhage

- ii. K26.2 Acute with hemorrhage and perforation
 - iii. K26.4 Chronic or unspecified with hemorrhage
 - iv. K26.6 Chronic or unspecified with hemorrhage and perforation
- 7. Peptic ulcer, site unspecified
 - i. K27.0 Acute with hemorrhage
 - ii. K27.2 Acute with hemorrhage and perforation
 - iii. K27.4 Chronic or unspecified with hemorrhage
 - iv. K27.6 Chronic or unspecified with hemorrhage and perforation
- 8. Gastrojejunal ulcer
 - i. K28.0 Acute with hemorrhage
 - ii. K28.2 Acute with hemorrhage and perforation
 - iii. K28.4 Chronic or unspecified with hemorrhage
 - iv. K28.6 Chronic or unspecified with hemorrhage and perforation
 - v. K29.01 Acute gastritis with bleeding
 - vi. K29.21 Alcoholic gastritis with bleeding
 - vii. K29.31 Chronic superficial gastritis with bleeding
 - viii. K29.41 Chronic atrophic gastritis with bleeding
 - ix. K29.51 Unspecified chronic gastritis with bleeding
 - x. K29.61 Other gastritis with bleeding
 - xi. K29.71 Gastritis, unspecified with bleeding
 - xii. K29.81 Duodenitis, with bleeding
 - xiii. K29.91 Gastroduodenitis, unspecified, with bleeding
- 9. K31.811 Angiodysplasia of stomach and duodenum with bleeding
- 10. K31.82 Dieulafoy lesion (hemorrhagic) of stomach and duodenum
- 11. K57.01 Diverticulitis of small intestine with perforation and abscess with bleeding
- 12. K57.11 Diverticulosis of small intestine without perforation or abscess with bleeding
- 13. K57.13 Diverticulitis of small intestine without perforation or abscess with bleeding
- 14. K57.21 Diverticulitis of large intestine with perforation and abscess with bleeding
- 15. K57.31 Diverticulosis of large intestine without perforation or abscess with bleeding
- 16. K57.33 Diverticulitis of large intestine without perforation or abscess with bleeding
- 17. K57.41 Diverticulitis of both small and large intestine with perforation and abscess with bleeding
- 18. K57.51 Diverticulosis of both small and large intestine without perforation or abscess with bleeding
- 19. K57.53 Diverticulitis of both small and large intestine without perforation or abscess with bleeding
- 20. K57.81 Diverticulitis of intestine, part unspecified, with perforation and abscess with bleeding
- 21. K57.91 Diverticulosis of intestine, part unspecified, without perforation or abscess with bleeding
- 22. K57.93 Diverticulitis of intestine, part unspecified, without perforation or abscess with bleeding
- 23. K62.5 Hemorrhage of anus and rectum
- 24. K63.81 Dieulafoy lesion of intestine
- 25. K92.0 Hematemesis
- 26. K92.1 Melena
- 27. K92.2 Gastrointestinal hemorrhage, unspecified

D. ANALYSIS METHODS FOR DISTRIBUTED NETWORKS

1. Meta-analysis

In meta-analysis, each Data Partner estimates the effect and their variance (or other information needed to calculate the weight) using pre-specified models on their own individual-level data and send these to the coordinating center. Then, the overall estimated effect and 95% confidence interval is derived by pooling site-specific estimates. A commonly used weight is inverse of variance on the log scale of the estimate. Meta-analysis method requires the least amount of data sharing and is flexible with respect the types of study design and analysis. However, it is the least flexible with respect to the subgroup and sensitivity analyses and requires greatest degree of programing/analysis ability at each participating site.

2. Case-centered Logistic Regression

In this method, each Data Partner transfers an aggregated dataset to the coordinating center that includes 1 record per risk set. Each risk set is anchored by a case (patient with the outcome of interest) and comprised of the cases and comparable individuals at risk of the outcome at the time the case occurs. Each record includes a binary variable indicating whether the patient diagnosed with the outcome is exposed to the treatment and the log odds of the site-specific proportion of exposed patients in the risk set. Confounding adjustment will be conducted through stratification. Specifically, if the number of imbalanced covariates is small, we will create strata that are defined by these covariates within each site; the risk set for a given case will be at-risk individuals who are within the same covariate stratum as the case. If the number of imbalanced covariates is large, we will create propensity score (PS) strata. The PS will be estimated within each site, and the risk set for a given case will be at-risk individuals who are within the same propensity score stratum as the case. The statistical team fits a logistic regression model with indicator variable as the dependent variable and log odds as the independent variable. It is shown that this method maximized the same likelihood as a stratified Cox model using patient-level data. Thus, it is appropriate for study designs that needs to be analyzed using Cox proportional hazards model.

3. Distributed Regression

Distributed regression is a suite of methods that enable researchers to conduct multi-database multivariable-adjusted regression analysis without the need to centrally combine all individual-level data from participating sites. It performs the same numeric algorithm as standard ordinary least squares regression but uses only summary statistics for computation. By following the same computation process, distributed regression and pooled individual-level data analysis produce statistically equivalent results. With distributed regression, we can adjust for imbalanced covariates directly in the outcome regression models.

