- 2. Time to OAC start: the time to first OAC initiation, as defined by the first fill date for apixaban, dabigatran, edoxaban, rivaroxaban, or warfarin. If there was no prescription fill for these medications, but the patient had 4 or more INR values measured over the study period, the date of the first INR measurement will be used for initiation of OAC.
- 3. OAC prescription coverage: the proportion of days that AF patients have OAC prescription fills over the duration of the study. The assumption is that a 30-day or 90-day supply will last for the planned period, even in the case of warfarin, when the length of time that a prescription lasts may be less well defined. Patients will only be included in this secondary analysis, if they had a prescription fill for apixaban, dabigatran, edoxaban, rivaroxaban, or warfarin.
- 4. OAC rates at follow-up: proportion of patients with an active oral anticoagulant dispensing at the end of the one-year follow-up. This will include patients with apixaban, dabigatran, edoxaban, rivaroxaban, or warfarin medication fills that encompass the end of the study period. If there was no prescription fill for these medications, this will also include patients with 4 or

more INR values measured over the study period, who had an INR value measured within 60 days of the end of the approximately one-year follow-up.

- 5. Rate of stroke or TIA: the incident rate of stroke or TIA related hospitalizations; stroke, excluding transient ischemic attacks (TIAs), will also be assessed
- 6. Rate of bleeding related hospitalization: the incident rate of hospitalizations for any bleeding
- 7. Health care utilization: the total counts of health care utilization (number of outpatient visits, emergency department visits, hospital admissions, etc.) for AF patients, including AF and non-AF related care
- 8. In-patient all-cause mortality: patients with in-hospital death
- 9. All-cause mortality: in a subset of patients with mortality status

XVI. STATISTICAL ANALYSES

A. DEMOGRAPHICS AND BASELINE CHARACTERISTICS

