5. Health Care Utilization	177
III. REFERENCES	188
IV. APPENDIX	199
A. TABLES.....	199
B. CONSORT 2010 WORKSHEET FOR RANDOMIZED TRIALS.....	33
C. ICD-10 CODES FOR DEFINING CLINICAL OUTCOMES	3735
D. ANALYSIS METHODS FOR DISTRIBUTED NETWORKS	39
1. Meta-analysis	39
2. Case-centered Logistic Regression	39
3. Distributed Regression	39

I. OVERVIEW

This is the statistical analysis plan (SAP) for **IM**plementation of a randomized controlled trial to im**Pr**ove treatment with oral **AntiCoagulanTs** in patients with **A**trial **F**ibrillation (IMPACT-AFib) study. The purpose of this document is to provide an overview of the study design and study objectives, outline the types of analyses and data presentations relevant to the study objectives, and to provide a detailed description of the methods in which the statistical analyses will be conducted to meet protocol objectives. This plan is a supplement to the materials provided in the IMPACT-AFib protocol. This SAP does not contain all the protocol details and is intended to be read in conjunction with the full protocol. Only analytic decisions are documented here.

A. PRIMARY ENDPOINT

IMPACT-AFib is a prospective randomized controlled clinical trial that will evaluate whether a patient and provider education intervention increases the proportion of patients with atrial fibrillation (AF) who fill at least one oral anticoagulant (OAC) over the course of follow-up. Follow up is through the date on which at least 80% of eligible study participants have at least 12 months of follow-up time. As described in the protocol, there is an “early intervention” arm (who receive patient and provider mailings) and a “delayed intervention” arm (who receive provider mailings only, ~12 months after the early intervention mailings occur).

B. SECONDARY ENDPOINTS

We will evaluate the impact of the patient and provider education intervention on the endpoints listed below at the end of follow-up (i.e., the date on which at least 80% of eligible study participants have at least 12 months of follow-up time):

- The incidence rate of stroke or transient ischemic attack (TIA) hospitalizations
- The incidence rate of stroke hospitalizations
- The time to first OAC prescription fill
- The proportion of days covered by OAC prescription fills
- Proportion of patients actively on OAC at 12 months of follow-up
- The incidence rate of hospitalization for any bleeding
- All-cause in-hospital mortality rates¹

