S₂	Prior stroke or TIA or thromboembolism	ICD-10-CM: I60.**, I60.2, I60.4, I60.6-I60.9, I61.*, I62.9, I63.0*, I63.0**, I63.1*, I63.1**, I63.2*, I63.2**, I63.3*, I63.3**, I63.4*, I63.4**, I63.5*, I63.5**, I63.6, I63.8, I63.9, I69.00, I69.0**, I69.10, I69.1**, I69.30, I69.3**, I69.8** except I69.898, I69.9** except I69.998, S06.34, S06.34*A, and S063.34*D, S06.35, S06.35*A, and S063.35*D, S06.36, S06.36*A, and S063.36*D, S06.6, S06.6X*A, S06.6X*D, Z86.73, H34.00, H34.219, H34.239, H34.9, I67.82, I74.**, I74.2-I74.9, K76.3, N28.0, T81.718A, G45.8, G45.9; ICD-9-CM: 438.0-438.8, 852.0, 853.0, 433.*1, 434.*1, 438.1*, 438.2*, 438.3*, 438.4*, 438.5*, 438.81-428.85, 852.0*, 853.0*, V12.54, 444, 444.*, 444.**, 453.9, 573.4, 362.30-362.34, 434.00, 435, 435.8, 435.9; CPT: 34101, 34111, 34201, 34203
V	Vascular disease (e.g. peripheral artery disease, myocardial infarction, aortic plaque)	ICD-10-CM²: E08.51, E08.52, E09.51, E09.52, E10.51, E10.52, E11.51, E11.52, E13.51, E13.52, I21.0*, I21.1*, I21.2*, I21.3, I21.4, I22.*, I25.7, I25.70-I25.73, I25.70*, I25.71*, I25.72*, I25.73*, I25.79, I25.79*, I25.810, I73.8, I73.9, I77.1, T82.2, T82.21 and subcodes, Z95.820, Z95.82
A	Age 65–74 years	
Sc	Sex category (i.e. female sex)	

Patients are excluded if they meet any of the following criteria:

1. Evidence of OAC medication fill during the 12 months prior to randomization (the delayed intervention group’s treatment status will be assessed at the end of the 12-month follow-up period)

² Only ICD-10-CM codes are presented for the vascular disease component given size of the list; complete code list, which includes ICD-9-CM, ICD-10-PCS, ICD-9-PCS, CPT, and HCPCS codes, is available on the [Sentinel website](#).

2. Conditions other than AF that require anticoagulation such as ever having mechanical prosthetic valve, deep venous thrombosis, or pulmonary embolism prior to the last date in the current approved data used for cohort identification (“ever” is operationalized as -6000 days from the index AF code)
3. Pregnancy identified within 6 months of the last date in the current approved data used for cohort identification
4. Any known history of intracranial hemorrhage prior to the last date in the current approved data used for cohort identification
5. Hospitalization for any bleeding within the last 6 months of the last date in the current approved data used for cohort identification

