1. 33% OAC initiation rate in the delayed intervention arm
2. 38% OAC initiation rate in the early intervention arm (5% absolute improvement in OAC initiation over the 33% OAC initiation expected in the delayed intervention arm over 1-year follow-up)
3. 1-year attrition rate: 30% dropout or lost-to-follow-up
4. Two-sided type I error rate of 0.05
5. Roughly 10,000 patients who meet the inclusion/exclusion criteria will yield more than 99% power to detect a 5% absolute difference

Power	Total sample size (2-arm)	Early Intervention	Delayed Intervention
90%	5610	2805	2805
95%	6910	3455	3455
99%	9718	4859	4859

2. Important Secondary Outcome of Stroke or TIA

A study with approximately 80,000 patients could provide reasonable power for stroke or TIA outcome under certain assumptions listed below:

- 1-year stroke or TIA rate: 18% among patients not treated with OAC
- 1-year stroke or TIA rate: 7% among patients treated with at least 1 OAC fill
- Duration of follow-up: 1 year
- 33% of delayed intervention patients will have at least 1 fill of OAC, meaning the 1-year stroke or TIA rate in the delayed intervention group would be 14.4%
- 1-year attrition rate: 30% dropout or lost-to-follow-up
- Two-sided type I error of 0.05
- If 38% of early intervention patients have at least 1 fill of OAC (meaning the 1-year stroke or TIA rate in the early intervention group would be 13.82%, i.e., an absolute reduction of 0.55%), the study will have 46% power to detect this 0.55% reduction. However, if 40.5% of early intervention patients have at least 1 fill of OAC (meaning the 1-year stroke or TIA rate in the

early intervention group would be 13.54%, i.e., an absolute reduction of 0.83%), the study will have 80% power to detect this 0.83% reduction.

8. The sample size has 80% power to detect a 0.5% absolute reduction in stroke, assuming a cumulative 1-year incidence of stroke of 4.2% in control (delayed intervention arm) patients and 3.7% in intervention (early intervention arm) patients. The assumption is that patients not on oral anticoagulation have an annual stroke rate of 5%, and stroke will be reduced by 50% (HR=0.5) in the treated (anticoagulated) population. The 80% power requires that 52% of early intervention arm patients are treated at 1-year as compared to 33% in the control arm.

II. STATISTICAL ANALYSIS

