The proportion of patients actively on OAC at the end of follow-up will be summarized and compared between the early intervention and delayed intervention arms. Last Observation Carried Forward will be used if the patient is censored. To evaluate whether the early patient-level and provider-level educational intervention increases the proportion of patients being actively on OAC at the end of follow-up, we will calculate the odds ratio (i.e., the odds of an average patient in the early intervention group being actively on OAC at the end of follow-up as compared to the odds of an average patient in the delayed intervention group being actively on OAC at the end of follow-up) using logistic regression model adjusted for baseline risk factors listed in Appendix A Table A, with GEE to account for the correlation of responses among the patients from a same service provider. The odds ratio, 95% confidence interval (CI) and p-value will be presented to show whether there is a statistically significant difference in the proportion of patients who are actively on OAC at the end of follow-up between the early intervention and delayed intervention groups. Each Data Partner will run the SAS program(s) distributed by HPHCI, developed with the statistical team at Duke DCC, to perform logistic regression analysis on their cohort of patients and return the parameter estimate (SE), estimated odds ratio, 95% confidence interval (CI) and p-value, shown in Table 6 in Appendix A (there will be one for each Data Partner), to HPHCI. Meta-analysis methods with inverse-variance weighting on log scale will be used to integrate the results and obtain the estimate of the overall odds ratio, 95% confidence interval and p-value for entire study population.

4. Clinical Outcomes

Claims data (ICD-10-CM codes used for defining these outcomes are listed in Appendix C) will be used to define the following clinical outcomes:

- Hospitalization for ischemic stroke or unknown stroke
- Hospitalization for TIA
- Hospitalization for systemic embolism
- Hospitalization for ischemic stroke, TIA or systemic embolism
- Hospitalization for hemorrhagic stroke
- Hospitalization for any bleeding
- Hospitalization for ischemic or hemorrhagic stroke
- Hospitalization for ischemic or hemorrhagic stroke or systemic embolism
- Composite of ischemic stroke, hemorrhagic stroke, and hospitalization for any bleeding
- All-cause in-hospital death

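### SAP Appendix C(a) counts TIA codes (G45.x) as ischemic or unknown stroke although the protocol separates stroke from TIA; Appendix C has no TIA heading and no systemic embolism codes

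*SAP*

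**What the plan says.** The protocol keeps two outcomes apart. Section V.B has stroke or TIA hospitalization as secondary objective 1 and stroke hospitalization as objective 2. Section XV, item 5, defines the first and adds that "stroke, excluding transient ischemic attacks (TIAs), will also be assessed". Section XVI.C lists stroke or TIA separately from ischemic or unknown stroke.

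The SAP repeats the separation. Section I.B lists "The incidence rate of stroke or transient ischemic attack (TIA) hospitalizations" and, on its own line, "The incidence rate of stroke hospitalizations". Section II.D.4 gives ischemic/unknown stroke, TIA and systemic embolism one line each and says that the "ICD-10-CM codes used for defining these outcomes are listed in Appendix C".

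Appendix C has four headings: (a) ischemic or unknown stroke, (b) hemorrhagic stroke, (c) any bleeding and (d) gastrointestinal bleeding. Item 6 of (a) is "G45.x Transient cerebral ischemic attacks and related syndromes, including" G45.0 to G45.4, G45.8 and G45.9. The only exclusion attached to (a) is a primary diagnosis of intracranial injury (S06.x). There is no heading for TIA or for systemic embolism. The opening line says that the codes will be used to define the outcomes and that the list is not final.

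**The concern.** A code list decides what a claims outcome measures. With G45.x inside list (a), an admission coded only as TIA is an ischemic/unknown stroke event, and the protocol's stroke outcome without TIA cannot be obtained from that row.

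The distributed design makes this harder to repair later. Each Data Partner runs the supplied program on its own data and returns only results, so TIAs cannot be taken out of the returned stroke counts afterwards. The sites would have to rerun.

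The gap for systemic embolism is simpler. The outcome and its composites are specified, II.D.4 points to Appendix C for the codes, and none are there.

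**Working it through.** **Side by side**

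- Protocol XV.5: stroke is also assessed with TIA left out.
- SAP II.D.4: TIA is its own outcome, and one composite names ischemic stroke, TIA and systemic embolism together. Naming TIA there adds nothing if ischemic stroke already contains G45.x.
- SAP Appendix C(a): G45.x is a stroke code, with no TIA exclusion.
- SAP Table 7, block that ignores the principal-diagnosis flag: the ischemic/unknown stroke row is followed by a row for ischemic stroke or TIA. If both use (a), and TIA means G45.x, the two rows count the same events.

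No reading of (a) as written keeps TIA out.

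**How many outcomes and rows**

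II.D.4 has 10 outcomes. Tables 7 and 8 each have 9 rows in the principal-diagnosis block and 10 in the flag-ignored block: 9 + 10 = 19.

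| Outcome | Rows per table | Contains G45.x? |
|---|---|---|
| Ischemic/unknown stroke | 2 | Yes, as written |
| Ischemic or hemorrhagic stroke | 2 | If it reuses (a) |
| The same plus systemic embolism | 2 | If it reuses (a) |
| Stroke-and-bleeding composite | 2 | If it reuses (a) |

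Certain: 1 of 10 outcomes and 1 × 2 = 2 of 19 rows per table. Conditional maximum: 4 of 10 outcomes and 4 × 2 = 8 of 19 rows per table. The condition is likely because Appendix C has no other ischemic list, but no passage states it. Under it, no row gives ischemic plus hemorrhagic stroke without TIA.

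**Do the documents give the size?**

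SAP I.G.2 plans the two endpoints separately. In the delayed arm, with 33% treated:

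- Stroke or TIA: 0.67 × 18% + 0.33 × 7% = 14.37%, which reproduces "meaning the 1-year stroke or TIA rate in the delayed intervention group would be 14.4" (percent).
- Stroke: the untreated risk is 5%. With HR 0.5 the treated risk is 1 − 0.95^0.5 = 2.53%. Then 0.67 × 5% + 0.33 × 2.53% = 4.19%, which reproduces "assuming a cumulative 1-year incidence of stroke of 4.2% in control" patients.

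The stated 80% power for stroke also reproduces. The early arm with 52% treated is 0.48 × 5% + 0.52 × 2.53% = 3.72%, and 40,000 × 0.7 = 28,000 are evaluable per arm. A two-sided 5% comparison of 4.19% with 3.72% has 81.3% power.

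The plan thus treats stroke and stroke or TIA as different endpoints. It gives no TIA hospitalization rate. As an assumption only, suppose G45.x adds 0.5, 1, 2 or 3 points to the stroke rate. Power is then:

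- if the intervention does not change TIA: 76.7%, 72.5%, 65.0% or 58.8%;
- if TIA falls by the same relative amount as stroke: 85.6%, 89.0%, 93.8% or 96.6%.

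The direction depends on an effect that the documents do not give. What is certain is that the endpoint changes.

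**Two further mismatches in the same outcome set**

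- The stroke-and-bleeding composite includes systemic embolism in Tables 7 and 8 but not in II.D.4.
- The note under Table 8 restricts its endpoints to principal discharge diagnoses, while Table 8 has a block that ignores that flag.

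**The case against.** The best defence is that Appendix C is marked as not final, so the codes may still change. That lowers the stakes, but it does not resolve the conflict in the current text, and the same sentence says that these codes will be used. It is also true that the same list applies to both arms, that the primary endpoint is untouched, and that the documents neither give codes for the composites nor say which row answers objective 2. These points stand, and they are why only the ischemic/unknown stroke outcome is certain to be affected.

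Several stronger readings are tempting, and the documents do not support them:

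- *That the gap between 14.4% and 4.2% is the TIA share.* The two figures come from planning scenarios with different assumed treatment effects (7/18 = 0.39 for stroke or TIA, HR 0.5 for stroke). Nothing says that the difference is TIA.
- *That the mix-up costs power.* The range above goes both ways.
- *That Appendix C contains no TIA codes.* It does, in item 6 of (a). They lack a heading of their own. Only systemic embolism has no codes at all.
- *That the CHA2DS2-VASc coding shows (a) to be too broad.* SAP Table 1 takes only two codes from G45 ("N28.0, T81.718A, G45.8, G45.9"), but that list scores prior history, includes sequelae and history codes, and need not match a list for incident admissions.
- *That the non-specific codes I67.89 and I67.9 are errors.* The heading of (a) covers unknown stroke, and no passage conflicts with them.

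**Conclusion.** Wrong as written. Appendix C(a) classes TIA as ischemic/unknown stroke, against Protocol XV.5 and against the SAP's own separate TIA outcome, and Appendix C lacks the systemic embolism codes that II.D.4 says it holds. The certain reach is 1 of 10 outcomes and 2 of 19 rows in each of Tables 7 and 8. It extends to 4 outcomes and 8 rows per table, and leaves objective 2 without a row, only if the composites reuse (a). The number of events that would be misclassified cannot be derived from the documents. The point should be fixed, but it is confined to secondary clinical outcomes, and nothing here indicates a difference in coding between arms.

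**What to change.** 1. Move G45.x out of Appendix C(a) into a separate TIA list.
2. Add a systemic embolism list.
3. State that every composite naming ischemic stroke uses the revised (a).
4. Name the row that answers objective 2 (stroke without TIA). Add or name a row for objective 1 (stroke or TIA) in II.D.4 and in both blocks of Tables 7 and 8; at present only the flag-ignored block of Table 7 comes close, with ischemic stroke or TIA.
5. Make the stroke-and-bleeding composite the same in II.D.4 and the tables.
6. Reconcile the note under Table 8 with its flag-ignored block.

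The cost is an edit to a list already marked as provisional, one outcome list and two table shells. No new data are needed and no sample-size figure changes. If the programs have already run at the Data Partners, the affected rows would need a rerun.
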